#### 5.1.1.3.2 Pharmacokinetic Analyses

Pharmacokinetic analyses will be described in a separate SAP.

# 5.1.1.3.3 Multiple Comparisons Procedure for Primary and Secondary Endpoints

The primary and secondary efficacy endpoints are identified as follows:

- Primary (P1): Change from baseline in mean monthly MPM headache days across the 12week treatment period
- 1st Secondary (S1): Change from baseline in mean monthly headache days across the 12week treatment period
- 2nd Secondary (S2): Proportion of patients with at least a 50% reduction in mean monthly MPM headache days across the 12-week treatment period

# • 3rd Secondary (S3): Change from baseline in mean monthly acute medication use days across the 12-week treatment period

The overall familywise error rate (FWER) will be controlled at  $\alpha = 0.05$  for each set of primary and secondary endpoint comparisons between each dose level of atogepant vs placebo. Specifically, the overall type I error rate for multiple comparisons across atogepant doses and the primary and secondary efficacy endpoints will be controlled at the 0.05 level using a graphical approach by Bretz et al (2011). The overall graphic approach procedure is defined in the *Table 5–15* and *Figure 5-1*. *In the graph, each of the nodes is corresponding to one null hypothesis, for example, 60BID/P1 represents the null hypothesis that there is no statistically significant difference comparing 60 mg BID versus placebo on the primary endpoint. The number inside each node is the proportion of overall alpha initially allocated to that hypothesis. The number on the edge between two nodes represents the proportion of local alpha propagated from one hypothesis to the other given the former null hypothesis is rejected.* 

It is of Sponsor's interest to develop a QD regimen for registration unless the BID regimen provides meaningful additional benefit. Therefore, this study is designed to identify the dose regimen of QD or BID for the future development along with using its results for registration. To accomplish that objective, the weighting strategy is designed to allocate initial alpha equally to the QD and BID dose regimen. Within QD or BID dose regimen, atogepant doses will be tested in a hierarchical order from high to low dose. Specifically, for QD regimen, 50% of overall alpha (i.e. 0.025) is allocated to 60QD/P1. If 60QD/P1 is statistically significant, 3/5 of the local alpha (i.e. 0.015) will be propagated to test the lower dose on primary endpoint (30QD/P1); and the other 2/5 of the local alpha (i.e. 0.01) will be passed to the same dose comparison for the secondary endpoint (60QD/S1). The proportion of weights are chosen to first ensure sufficient power for the lower dose comparison on primary hypothesis and then reserve the rest of the alpha for the corresponding secondary endpoints so that their data can be used as part of the registration along with primary data. Then if 30QD/P1 is significant, 1/3 of the local alpha (i.e. 0.005) will be propagated to test 10QD/P1; and the other 2/3 of the local alpha (i.e. 0.01) will be passed to 30QD/S1. Similar weighting strategy applies to the BID regimen (60 mg BID and 30 mg BID).

Following statistical significance of primary endpoint for 60 mg QD and 30 mg QD, if 60QD/S1, 30QD/S1, 10QD/P1, or 10QD/S1 is significant, 100% of the local alpha will then be passed sequentially for the remaining secondary endpoints. Finally, if 60 mg QD or 30 mg QD can be shown significant across primary and all secondary endpoints, the associated alpha will be recycled to the primary hypothesis comparing the next lower dose. Similar alpha propagation applies to the secondary endpoints of BID regimen (60 mg BID and 30 mg BID). By this weighting strategy, secondary endpoints would be tested at the same alpha level of 0.01 for all 5 atogepant doses after the corresponding primary hypothesis is rejected (without considering alpha recycling). Under this strategy, no secondary hypothesis can be rejected until a primary hypothesis of the corresponding dose comparison is rejected. The primary endpoint will serve as the gatekeeper for the secondary endpoints. Weighted Bonferroni tests will be used for testing the hypotheses in the graph.

In addition, 10 mg QD dose comparison is tested with control of type I error. In case the other four higher doses are all rejected, 10QD/P1 will be tested at alpha level of 0.01. A lower expected alpha level is allocated to the 10QD/P1 is because this dose is included in the study as a potentially sub-optimal dose.

Nodes	Alternate Hypothesis	Weight	Initial Local Significance Level
60mgBID P1	60 mg BID atogepant is significantly different from placebo in change from baseline in mean monthly MPM headache days across the 12-week treatment period (P1)	1/2	$\alpha^*(1/2) = \alpha/2$
30mgBID P1	30 mg BID atogepant is significantly different from placebo in change from baseline in mean monthly MPM headache days across the 12-week treatment period (P1)	0	$\alpha * \theta = \theta$
60mgQD P1	60 mg QD atogepant is significantly different from placebo in change from baseline in mean monthly MPM headache days across the 12- week treatment period (P1)	1/2	$\alpha^*(1/2) = \alpha/2$
30mgQD P1	30 mg QD atogepant is significantly different from placebo in change from baseline in mean monthly MPM headache days across the 12- week treatment period (P1)	0	$\alpha * \theta = \theta$
10mgQD P1	10 mg QD atogepant is significantly different from placebo in change from baseline in mean monthly MPM headache days across the 12- week treatment period (P1)	0	$\alpha * 0 = 0$
60mgBID S1	60 mg BID atogepant is significantly different from placebo in change from baseline in mean monthly headache days across the 12- week treatment period (S1)	0	$\alpha * \theta = \theta$
30mgBID S1	30 mg BID atogepant is significantly different from placebo in change from baseline in mean monthly headache days across the 12- week treatment period (S1)	0	$\alpha * \theta = \theta$
60mgQD S1	60 mg QD atogepant is significantly different from placebo in change from baseline in mean monthly headache days across the 12-week treatment period (S1)	0	$\alpha * \theta = \theta$
30mgQD S1	30 mg QD atogepant is significantly different from placebo in change from baseline in mean monthly headache days across the 12-week treatment period (S1)	0	$\alpha * 0 = 0$
10mgQD S1	10 mg QD atogepant is significantly different from placebo in change from baseline in mean monthly headache days across the 12-week treatment period (S1)	0	$\alpha * 0 = 0$
60mgBID S2	60 mg BID atogepant is significantly different from placebo in proportion of patients with at least a 50% reduction in mean monthly MPM headache days across the 12-week treatment period	0	$\alpha^*\theta=\theta$

 Table 5–15
 Multiple Comparisons Procedure Definitions

Nodes	Alternate Hypothesis	Weight	Initial Local Significance Level
30mgBID S2	30 mg BID atogepant is significantly different from placebo in proportion of patients with at least a 50% reduction in mean monthly MPM headache days across the 12-week treatment period	0	$\alpha * \theta = \theta$
60mgQD S2	60 mg QD atogepant is significantly different from placebo in proportion of patients with at least a 50% reduction in mean monthly MPM headache days across the 12-week treatment period	0	$\alpha * \theta = \theta$
30mgQD S2	30 mg QD atogepant is significantly different from placebo in change from baseline in proportion of patients with at least a 50% reduction in mean monthly MPM headache days across the 12-week treatment period	0	$\alpha * 0 = 0$
10mgQD S2	10 mg QD atogepant is significantly different from placebo in proportion of patients with at least a 50% reduction in mean monthly MPM headache days across the 12-week treatment period	0	$\alpha * 0 = 0$
60mgBID S3	60 mg BID atogepant is significantly different from placebo in change from baseline in mean monthly acute medication use days across the 12-week treatment period	0	$\alpha * \theta = \theta$
30mgBID S3	30 mg BID atogepant is significantly different from placebo in change from baseline in mean monthly acute medication use days across the 12-week treatment period	0	$\alpha * \theta = \theta$
60mgQD S3	60 mg QD atogepant is significantly different from placebo in change from baseline in mean monthly acute medication use days across the 12-week treatment period	0	$\alpha^*\theta = \theta$
30mgQD S3	30 mg QD atogepant is significantly different from placebo in change from baseline in mean monthly acute medication use days across the 12-week treatment period	0	$\alpha * 0 = 0$
10mgQD S3	10 mg QD atogepant is significantly different from placebo in change from baseline in mean monthly acute medication use days across the 12-week treatment period	0	$\alpha * 0 = 0$

#### 5.1.1.4 Safety Analyses

Safety analyses will be based on the Safety Population.

Baseline assessments for applicable safety endpoints defined as follows:

 Table 5–16
 Safety Endpoint Baseline Definitions

Parameter	Description	Timing
Clinical laboratory evaluations	eCRF- or (standardized) vendor-provided	Latest non-missing
Vital signs	assessments	assessment before
• Electrocardiograms (ECGs)		the first dose of
Č ( )		study medication

#### 5.1.1.4.1 Study Treatment Exposure and Compliance

Study treatment exposure and compliance will be summarized by treatment group for the Safety Population as follows:

Table 5–17	Study Treatment Summaries		
Parameter	Description	Timing	Methodology

Parameter	Description	Timing	Methodology
Study treatment	Treatment end date - treatment start date + 1	Treatment Period	Continuous
exposure (days) ¹			descriptives
Participant-years of	Sum over participants of study treatment	Treatment Period	—
study treatment	exposure		
exposure (years)			
Categorical study	• 1 day	Treatment Period	Categorical
treatment exposure	• 2-7 days		descriptives
	• 8-14 days		
	• 15-21 days		
	• 22-28 days		
	• 29-35 days		
	• 36-42 days		
	• 43-49 days		
	• 50-56 days		
	• 57-63 days		
	• 64-70 days		
	
 
71-77 days
 
		
	78-84 days		
	$\sim$ 78-64 days		
	• > 64 days		
Study treatment	Summary by visit interval and overall	Day 1 – Week 2,	Continuous
compliance $(\%)^2$		Week 2 – Week 4,	descriptives
	Number of treatment units	Week 4 – Week 6,	
	100 ×actually taken	Week 6 – Week 8,	
	Number of treatment units	Week 8 – Week 12,	
	expected to be taken	Overall during	
		Treatment Period	
Categorical study	Summary by the following compliance	Day 1 – Week 2,	Categorical
treatment compliance	categories:	Week 2 – Week 4,	descriptives
(%)	• < 80%	Week 4 – Week 6,	
	• 80% - 120%	Week 6 – Week 8,	
	• > 120%	Week 8 – Week 12,	
		Overall during	
		Treatment Period	

¹ Treatment dosing data will be listed. ² Treatment duration and compliance will be listed.

#### 5.1.1.4.2 **Adverse Events**

The following adverse event (AE) terms are defined:

Table 5–18	AE Terms

Term	Description
Treatment-	An event that initially occurs or increases in severity on or after the treatment start date, where:
emergent	
 
Treatment start date ≤ event start date ≤ (treatment end date + 30 or Visit 8, whichever comes later)
 

On-therapy	An event where:
	
 
Treatment start date ≤ event start date ≤ (treatment end date + 30 or Visit 8, whichever comes later)
 

Newly	An event that initially occurs or increases in severity on or after the start date of safety follow-up
emergent	period, where

Term	Description
	• Start date of the safety follow-up period $\leq$ event start date $\leq$ (treatment end date + 30 or
	Visit 8, whichever comes later)

AEs, encompassing abnormalities and surgeries reported as occurring after the Screening Visit, will be coded using MedDRA version 19.0 or newer. Unique participants reporting AEs in the following AE categories will be summarized by treatment group for the Safety Population as follows:

Parameter	Description	Timing	Methodology
Overall summary	
 
Overall summary only for the following categories:
 
Treatment-emergent AEs (TEAEs)
 
Treatment-related TEAEs
 
On-therapy serious adverse events (SAEs)
 
On-therapy fatal SAEs
 
AEs leading to discontinuation
 
	From treatment start date until 30 days after treatment end date or Visit 8, whichever comes later	Categorical descriptives
TEAEs	Overall summary and by SOC and PT	From treatment start date until 30 days after treatment end date or Visit 8, whichever comes later	Categorical descriptives
Common TEAEs	
 
Summary by PT
 
Includes TEAEs occurring in ≥ 2% of participants in any treatment group
 
	From treatment start date until 30 days after treatment end date or Visit 8, whichever comes later	Categorical descriptives
TEAEs by severity	
 
Overall summary and by SOC, PT, and severity
 
Participants categorized overall and within each SOC and PT for the most severe occurrence
 
	From treatment start date until 30 days after treatment end date or Visit 8, whichever comes later	Categorical descriptives
TEAE by relationship	
 
Overall summary and by SOC, PT, and relationship
 
Participants categorized overall and within each SOC and PT for the most related occurrence
 
	From treatment start date until 30 days after treatment end date or Visit 8, whichever comes later	Categorical descriptives
Newly emergent AE	Overall summary and by SOC and PT	From safety follow- up start date until 30 days after treatment end date or Visit 8, whichever comes later	Categorical descriptives
On-therapy SAE ¹	Overall summary and by PT	From treatment start date until 30 days	Categorical descriptives

Table 5–19AE Summaries

Parameter	Description	Timing	Methodology
		after treatment end	
		date or Visit 8,	
		whichever comes	
		later	
Newly emergent SAE	Overall summary and by PT	From safety follow-	Categorical
		up start date until 30	descriptives
		days after treatment	
		end date or Visit 8,	
		whichever comes	
		later	
On-therapy fatal SAE ¹	Overall summary and by PT	From treatment start	Categorical
		date until 30 days	descriptives
		after treatment end	
		date or Visit 8,	
		whichever comes	
		later	
Newly emergent fatal	Overall summary and by PT	From safety follow-	Categorical
SAE		up start date until 30	descriptives
		days after treatment	
		end date or Visit 8,	
		whichever comes	
		later	
AEs leading to	Overall summary and by PT	From treatment start	Categorical
discontinuation ¹		date until 30 days	descriptives
		after treatment end	
		date or Visit 8,	
		whichever comes	
		later	

¹ Participants who report  $\geq$  1 AE in the AE category and all AEs for those participants will be listed. SOCs will be sorted alphabetically; PTs will be sorted in descending frequency in the highest dose group.

Allergan Confidential

#### 5.1.1.5 **Subgroup Analyses**

Not applicable.

#### **Interim Analyses** 5.1.1.6

Not applicable.

#### 5.1.2 **Determination of Sample Size**

With this multiplicity strategy as described in Section 5.1.1.3.3, the assumptions and corresponding power assessments for the primary efficacy endpoint are shown in Table 5–25. The treatment differences are assumed based on results from other episodic migraine prevention studies. The placebo-adjusted reduction in monthly migraine days observed from other episodic migraine prevention studies ranged from 1.1 to 2 days [topiramate (Silberstein 2004 and Brandes 2004), telcagepant (Ho 2014), and CGRP monoclonal antibodies Ph2 studies (Dodick 2014; Dodick 2014; Sun 2016), and their Ph3 studies results reported from American Headache Society & American Academy of Neuroscience 2017]. Power is calculated via 10,000 simulations based on multiplicity adjustment as described in Figure 5-1 for the 5 doses and primary and secondary endpoints.

Table 5–25	Assumed Effect Size and Estimated Power for Primary Efficacy Endpoint				
	60 mg BID (n=90)	30 mg BID (n=90)	60 mg QD (n=180)	30 mg QD (n=180)	10 mg QD (n=90)
Assumed Treatment difference vs. placebo (placebo n = 180)	-1.6	-1.5	-1.5	-1.4	-1.2
Effect size (Common SD ¹ = 3.0)	0.53	0.5	0.5	0.47	0.4
Power	97.0%	91.4%	99.3%	98.1%	80.3%

¹ Common standard deviation is estimated based on blinded interim data assessments.

QD = once daily; BID = twice daily; SD = standard deviation.

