7.7 Sample Size Calculation

The assumptions and corresponding power assessments for the primary efficacy endpoint are shown in the table below. The treatment difference assumption is based on results from other episodic migraine prevention studies: the placebo-adjusted reduction in monthly migraine days ranged from 1.1 to 2 days (topiramate [Silberstein et al, 2004 and Brandes et al, 2004], telcagepant [Ho et al, 2014], and CGRP monoclonal antibodies Ph2 studies [Dodick et al, 2014; Dodick et al, 2014; Bigal et al, 2015; Sun et al, 2016], and their Ph3 studies results reported from [American Headache Society & American Academy of Neuroscience 2017](#)). Common standard deviation is estimated based on blinded interim data assessments of this study. Power is calculated via 10,000 simulations based on multiplicity adjustment.

	60mg BID (n=90)	30mg BID (n=90)	60mg QD (n=180)	30mg QD (n=180)	10mg QD (n=90)
Assumed Treatment difference vs. placebo (placebo n = 180)	-1.6	-1.5	-1.5	-1.4	-1.2
Effect size (Common SD = 3.0)	0.53	0.5	0.5	0.47	0.4
Power	97.0%	91.4%	99.3%	98.1%	80.3%

QD = once daily; BID = twice daily; SD = standard deviation.

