4.1 Study Design Summary

This is a multi-center, randomized, double-blind, placebo-controlled, parallel group study conducted at approximately 75 sites in the United States. Approximately 810 participants will be randomized to one of six treatment arms (placebo, 10-mg once daily [QD], 30-mg QD, 30-mg twice daily [BID], 60-mg QD, and 60-mg BID) in a 2:1:2:1:2:1 ratio as follows:

- Placebo (n = 180)
- Atogepant 10-mg QD (n = 90)
- Atogepant 30-mg QD (n = 180)
- Atogepant 30-mg BID (n = 90)
- Atogepant 60-mg QD (n = 180)
- Atogepant 60-mg BID (n = 90)

To maintain the blind, investigational product will be administered orally BID for 12 weeks to all participants. Participants, therefore, will receive either placebo twice daily, a morning dose of atogepant with an evening dose of placebo, or atogepant twice daily.

Subject participation will begin with a 4-week Screening/Baseline Period. Participants who complete the 4-week Screening/Baseline Period and meet all entry criteria will be randomized to the double-blind treatment period of the study at Visit 2 (randomization visit). The double-blind treatment period will last 12 weeks, with a subsequent Safety Follow-up Period of 4 additional weeks. There will be 8 scheduled clinic visits: Visit 1 (Screening/Baseline), Visit 2 (Randomization), Visit 3 (Week 2), Visit 4 (Week 4), Visit 5 (Week 6), Visit 6 (Week 8), Visit 7/ET (Week 12), and Visit 8 (Safety Follow-up). For details, please see Table 4–2, Schedule of Visit and Procedures.

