#### 5.1.1.3 Efficacy and Pharmacokinetic Analyses

Efficacy analyses will be based on the mITT Population.

The following efficacy assessments and terms are defined:

For analyses of headache characteristics and acute medication use, the first 28 days of the screening period, starting with the day of the screening visit, will serve as the "baseline". Baseline assessments for applicable efficacy endpoints defined as follows:

Table 5–13Efficacy Endpoint Baseline Definitions			
Endpoint	Description	Timing	
Baseline number of MPM headache days	The total number of reported MPM headache days divided by the total number of days with non-missing eDiary records during the 4-week baseline period and multiplied by 28. Refer to Section 6.4.1 for details.	The first 28 days from screening visit to the day before randomization	
Baseline number of headache days	The total number of reported headache days divided by the total number of days with non- missing eDiary records during the 4-week baseline period and multiplied by 28. Refer to Section 6.4.1 for details.	The first 28 days from screening visit to the day before randomization	
Baseline average headache day pain intensity	Baseline average headache day pain intensity is calculated for days with non-missing eDiary data during baseline period. Refer to Section 6.4.1 for details.	The first 28 days from screening visit to the day before randomization	
Baseline cumulative headache hours	Average daily headache hours are calculated for days with non-missing eDiary data during baseline period. Baseline cumulative headache hours are calculated as average daily headache hours multiplied by 28. Refer to Section 6.4.1 for details.	The first 28 days from screening visit to the day before randomization	
Baseline number of acute medication use days	The total number of reported acute medication use days divided by the total number of days with non-missing eDiary records during the 4- week baseline period and multiplied by 28. Refer to Section 6.4.1 for details.	The first 28 days from screening visit to the day before randomization	
Baseline number of triptan use days	The total number of reported triptan use days divided by the total number of days with non- missing eDiary records during the 4-week baseline period and multiplied by 28. Refer to Section 6.4.1 for details.	The first 28 days from screening visit to the day before randomization	

MPM = migraine/probable migraine.

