## 6.4.2 Primary Efficacy Analysis

The primary efficacy endpoint is the change from baseline in mean monthly MPM headache days across the 12-week treatment period. The endpoint will be analyzed using MMRM. The response variable is the change from baseline to each postbaseline month in monthly MPM headache days. The model will include baseline monthly MPM headache days as a covariate, treatment group and visit (month) as fixed factors, and treatment group-by-visit and baselineby-visit as interaction terms. The analysis will be performed based on evaluable postbaseline data using only the observed cases without imputation of missing values.

Restricted maximum likelihood method will be used. The within-patient correlation will be modeled using the unstructured covariance matrix. If the model does not converge, then the compound symmetry covariance structure will be used. The Kenward-Roger approximation will be used to estimate denominator degrees of freedom. Contrasts will be constructed to obtain the average treatment effects across the 12-week treatment period to compare each atogepant treatment group versus the placebo group. Each treatment effect and treatment comparisons will be estimated by the LS Means and their differences in LS Means, along with their SE and 95% confidence intervals, and the p-value corresponding to the betweentreatment group difference.

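### Is the 80.3% power for 10 mg QD unsupported because the secondary-endpoint inputs and an allowance for non-evaluable patients are not printed?

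*SAP*

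**What the plan says.** SAP 5.1.2 and Protocol 7.7 carry the same power table. The row labelled "Assumed Treatment difference vs. placebo (placebo n = 180") gives differences of -1.6 (60 mg BID), -1.5 (30 mg BID), -1.5 (60 mg QD), -1.4 (30 mg QD) and -1.2 (10 mg QD). The SD is 3.0, and each column carries n = 90 or n = 180. Stated power is 97.0, 91.4, 99.3, 98.1 and 80.3%. The SAP footnote on the SD reads "Common standard deviation is estimated based on blinded interim data assessments".

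Protocol 7.7 says only "Power is calculated via 10,000 simulations based on multiplicity adjustment". SAP 5.1.2 adds that the simulation covered the secondary endpoints as well: "Power is calculated via 10,000 simulations based on multiplicity adjustment as described in Figure 5-1 for the 5 doses and primary and secondary endpoints".

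SAP 5.1.1.3.3 sets out the testing graph. Each 60 mg primary test starts at 0.025. Part of the alpha moves down to the lower dose's primary test, and part moves to the secondaries of the same dose. Once a dose has won its primary and all three secondaries, "the associated alpha will be recycled to the primary hypothesis comparing the next lower dose". Before recycling, 10 mg QD is tested at 0.01 if all four higher doses have been rejected.

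On numbers, SAP 4.1 says "Approximately 810 participants will be randomized to one of six treatment arms", and its arm sizes are those in the power table. On analysis, "Efficacy analyses will be based on the mITT Population", and the primary MMRM is run "using only the observed cases without imputation of missing values".

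**The concern.** Recycled alpha reaches 10 mg QD only if higher doses win their secondary endpoints. The 80.3% therefore depends on assumed secondary effects that neither document prints, and a reader cannot rerun the column from the table. The arm sizes are also the randomised numbers, while the analysis uses a subset with evaluable diary data, so the simulation appears to treat every randomised patient as evaluable.

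If the hidden inputs were optimistic, 10 mg QD would be less well powered than it looks. A non-significant result in that arm could then be over-read as evidence against the dose, in a study that lists dose/response among its objectives (Protocol 2.1).

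**Working it through.** **Inputs.** Differences, SD 3.0 and n come from SAP Table 5-25. Tests are two-sided (SAP 5.1.1.1.3). Alpha weights come from SAP 5.1.1.3.3.

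**Formula for a fixed level.** Power = Φ( Δ / [SD·√(1/n₁ + 1/n₀)] − z(1−α/2) ).

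**1. The plan's own figures that need no secondary input.**
- 60 mg BID, α = 0.025: SE = 3.0·√(1/90 + 1/180) = 0.3873; 1.6/0.3873 = 4.131; 4.131 − 2.241 = 1.890; power 97.06% (stated 97.0%).
- 60 mg QD, α = 0.025: SE = 3.0·√(2/180) = 0.3162; 1.5/0.3162 = 4.743; 4.743 − 2.241 = 2.502; power 99.38% (stated 99.3%).

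Both reproduce at the printed n. The n behind the simulation is therefore stated: it is the randomised n.

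**2. 10 mg QD at fixed levels.** 1.2/0.3873 = 3.098.

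| α | Power |
|---|---|
| 0.005 | 61.5% |
| 0.01 | 69.9% |
| 0.025 | 80.4% |
| 0.05 | 87.3% |

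The stated 80.3% corresponds to a fixed level of about 0.0247, between the 0.01 available before recycling and the 0.05 that arrives if every higher-dose hypothesis is rejected.

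**3. The whole graph.** I rebuilt it from the prose of SAP 5.1.1.3.3, with a shared placebo arm. The standardised secondary effects are assumed to be a common ratio of the primary effect, and the between-endpoint correlation is also assumed.

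| Setting | 10 mg QD power |
|---|---|
| No recycling | 68.7% |
| Ratio 0.5, correlation 0.3 to 0.7 | 70.2 to 71.3% |
| Ratio 0.8, correlation 0.3 to 0.7 | 79.6 to 80.5% |
| Ratio 1.0, correlation 0.3 to 0.7 | 84.5 to 84.8% |
| All secondaries always won | 86.4% |

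Like for like, recycling supplies 80.3 − 68.7 = 11.6 points. The secondary effect size drives this. At ratio 0.8, moving the correlation from 0.3 to 0.7 changes power by 0.9 point. At ratio 0.8 and correlation 0.5, all five columns fall within 0.34 point of the table; the Monte Carlo standard error of 10,000 runs at 80.3% is √(0.803·0.197/10,000) = 0.4 point.

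The 30 mg columns are not sensitive. From no recycling to all secondaries won, 30 mg BID goes from 90.3 to 92.5% (stated 91.4%) and 30 mg QD from 97.2 to 98.1% (stated 98.1%).

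One edge, from the last 30 mg BID secondary to the 10 mg QD primary, is inferred because Figure 5-1 is not visible in the public text. Without it, 10 mg QD is 77.7 to 78.4% at ratio 0.8, 80.1 to 80.6% at 0.9 and 81.6 to 81.7% at 1.0. The figure is still attainable, at a ratio near 0.9.

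**4. Non-evaluable patients.** No rate is given, so this is a range under assumed uniform loss, ratio 0.8 and correlation 0.5.

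| Loss | 10 mg QD | 60 mg BID | 60 mg QD |
|---|---|---|---|
| 0% | 79.8% | 97.1% | 99.4% |
| 5% | 76.8% | 96.3% | 99.1% |
| 10% | 73.5% | 95.3% | 98.8% |

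A partial offset is possible. If the blinded SD pools over arms, it includes between-arm variance. Under the table's effects and the 2:1:2:1:2:1 allocation, the mean effect is 10.1/9 = 1.122 and the mean square is 14.67/9 = 1.630, so that variance is 1.630 − 1.122² = 0.371. The within-arm SD is then √(9.0 − 0.371) = 2.94, worth 0.371/9.0 = 4.1% of the sample. The documents do not say how the SD was pooled, so this is only a possibility.

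**The case for a change.** The strongest argument for a change is that a printed number should be reproducible from printed inputs, and the 10 mg QD figure is not. Several different sets of secondary effects reach about 80.3%, so the assumptions cannot be inferred backwards. Protocol 3.1 calls the smaller arms adequately powered, and superiority of 10 mg QD is among the objectives in Protocol 2.1. If higher-dose secondaries failed, the dose could be tested at 0.005 or 0.01, with power of 61.5% or 69.9%. The inputs must have been chosen to run the simulation, so printing them would be cheap.

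The omission is real, and so is the 11.6-point dependence. The consequence is thin. SAP 5.1.1.3.3 already discloses the recycling, gives the 0.01 level and says that 10 mg QD receives less alpha because it may be sub-optimal; a reader can compute 69.9% from what is printed. A non-significant 10 mg QD result will be judged on its estimate, its confidence interval (SAP 6.4.2) and the level it was actually tested at, not on planning power.

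The evaluability point is weaker still. The 20-of-28-day baseline diary rule is an entry criterion, and a dosed patient stays in the mITT set with a single post-baseline period of at least 12 diary days. The MMRM keeps anyone with one post-baseline value. A uniform cut in n does not model that partial-data pattern, and the documents supply no loss rate.

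**Conclusion.** No change is needed. The table omits the secondary effects and any evaluability allowance, and about 11.6 of the 80.3 points for 10 mg QD rest on the former. Yet 80.3% lies inside the attainable range of roughly 68.7 to 86.4% and is reached with secondary effects near 0.8 times the primary (near 0.9 without the inferred edge). No arithmetic error and no shortfall from the design's stated power has been shown.

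The clinical hypothesis in Protocol 2.2 concerns 60 mg QD or 60 mg BID, whose power reproduces from the printed inputs and stays above 95% at an assumed 10% loss. Listing the extra inputs would be tidy documentation, but it would leave every test, alpha level, patient number and conclusion as it is.

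This rests on the graph as rebuilt from the SAP's prose and on assumed secondary effects, correlations and loss rates.
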